2.1.3 Other Objectives

Not applicable.

2.2 Endpoints

2.2.1 Primary Endpoint

Responder rate to treatment at end of treatment or latest at week 12 as indicated by improvement on a seven-point Patient Global Assessment (PGA) scale where the patient is able to evaluate the overall change in her/his IC/BPS condition as markedly improved, moderately improved, slightly improved, no change, slightly worse, moderately worse or markedly worse. For the primary analysis, a responder is defined as a patient who has experienced an improvement on the PGA scale (i.e., PGA evaluated as markedly improved, moderately improved, or slightly improved. In case of slightly improved, patients will only be considered as responder if the question "Did therapy have a positive effect on your life and would you undergo this treatment again?" is answered with "Yes").

2.2.2 Secondary Endpoints

The secondary endpoints of the study are:

- Morning voiding volume over time (from patient diaries, until month 6).
- Total number of voids and total voiding volume (daytime and nighttime) over the last 24 hours (from patient diaries, until month 6)
- Change from baseline to end of treatment or latest to week 12 and to month 6 in Bladder Pain/Interstitial Cystitis Symptom Score (BPIC-SS).
- Percent responders at month 6 as indicated by improvement on the 7-point Patient Global Assessment (PGA) scale using the same responder definition as for the primary endpoint.
- Percent responders at end of treatment or latest at week 12 and at month 6 as indicated by improvement on the 7-point Patient Global Assessment (PGA) scale using an alternative responder definition (i.e. a responder is defined as a patient who experiences moderate or marked improvement).

- Change from baseline to end of treatment or latest to week 12 and to month 6 in bladder pain and urinary urgency on Visual Analogue Scale (VAS) scored from 0 to 100.
- Change from baseline to end of treatment or latest to week 12 and to month 6 in quality of life (QoL) on Visual Analogue Scale (VAS) scored from 0 to 100.
- Use of concomitant IC/BPS and pain medication count (until month 6).
- Occurrence of flares (documented as adverse events) and additional BPIC-SS (at the time of occurrence) (until month 6).
- Premature termination of treatment.
- Safety assessments: Adverse events and incidents (until month 6).

2.2.3 Other Endpoints (Efficacy)

Not applicable.

3 STUDY DESIGN

3.1 Overall Design

The present study is a prospective, multicenter, non-interventional study to be conducted in several European countries. It is planned to include approximately 15 study sites. The recruitment will be competitive, with a maximum of approximately 15 patients per site.

Due to the known difficulties with the diagnosis of IC/BPS, only clinical sites using state of the art diagnostic measures according to current therapeutic guidelines will be selected for this study.

3.2 Rationale for Study Design

Real world evidence observational studies are considered as an expedient tool to reflect the use of a product under real life conditions. However, due to the known difficulties with the diagnosis of IC/BPS, only clinical sites using state of the art diagnostic measures according to current therapeutic guidelines will be selected for this study.

A previous randomized, placebo-controlled trial with Cystistat showed limitations of using a placebo group. In this study, the initial response rate in the placebo group was higher than in the Cystistat group, with a turnaround of results at a later timepoint. Several possible explanations for these unexpected findings have been published (8). As the most likely reason for the placebo efficacy the possible beneficial effect from the alkalinizing placebo solution has been assumed.

Based on these considerations and on the known difficulties in recruiting high number of patients in this indication, an observational real world evidence study was chosen as the best feasible way to collect additional data to demonstrate the benefit/risk profile of Cystistat and compliance with the safety and performance requirements of the Medical Device Regulation (MDR) (11, 12).

3.3 End of Study Definition

The end of study is defined as the date of the last visit (or remote contact) of the last patient included in the study.

Cystistat will be instilled into the bladder according to the instructions for use (13). The observation period for a patient in this study will end approximately 6 months after start of treatment (irrespective of the duration of treatment). If required, treatment will be continued thereafter under regular medical care.

4 STUDY POPULATION

4.1 Study Population

Approximately 74 female patients with IC/BPS should be included in the study.

4.2 Inclusion and Exclusion Criteria

4.2.1 Inclusion Criteria

To be eligible for inclusion, a patient must comply with all of the following criteria:

- First prescription of Cystistat according to instructions for use.
- Female patients of any ethnic origin with clinical diagnosis of interstitial cystitis (IC)/bladder pain syndrome (BPS). If in accordance with routine clinical practice at the site, ESSIC diagnostic criteria will be used.
- Age: 18 years and older.
- At least 6 months duration of bladder pain/discomfort symptom(s), e.g. constant bladder pain/discomfort or bladder pain/discomfort when voiding or as a burning sensation between voids as the bladder fills with urine.
- At least one accompanying intermittent or persistent lower urinary tract symptom, such as urinary frequency, urgency, or nocturia during the previous 6 months.
- Bladder Pain/ Interstitial Cystitis Symptom Score (BPIC-SS) > 18 prior to first treatment
- Written informed consent.

4.2.2 Exclusion Criteria

The patient is not eligible for participating in this study, if one or more of the following criteria are met:

- Known hypersensitivity reactions to sodium hyaluronate.
- Pregnancy / planned pregnancy or breastfeeding during the course of this NIS.
- Known history of any GAG substitution therapy within the last 2 years.

- Known history of fulguration or resection of Hunner's lesions.
- Known diagnosis of recurrent urinary tract infection or overactive bladder.
- Any other conditions or diseases that can cause similar symptoms, using information from medical history, physical examination findings, laboratory studies (e.g., urine bacterial culture), and other previously performed procedures (e.g., urodynamics, cystoscopy, laparoscopy, radiological studies).
- Patients are not able to fulfil study requirements according to physician's opinion.

4.2.3 Criteria for Study Treatment Termination, Withdrawal from the Study and Study Termination

Patients may terminate the treatment with the investigational medical device or withdraw from the study at any time and for any reason without prejudice to their future medical care by the investigator or the study center. When available, a reason for not completing the study will be recorded in the electronic case report form (eCRF).

After enrolling in the study, patients will come to the study site on a weekly basis up to week 12 for the instillation of Cystistat according to the instructions for use (13). If required, treatment will be continued thereafter under regular medical care. A follow-up visit is scheduled for approximately month 6 as an on-site visit if in accordance with routine clinical practice. If not possible as an on-site visit, the information will be collected remotely (e.g., via phone and postal mail) from the patient.

Possible reasons for not completing the study may include, but are not limited to, the following:

- The patient withdraws consent.
- Diagnosis of pregnancy or stated intention to become pregnant.
- At the investigator's discretion, if it is in the patient's best interest due to occurrence of an AE or other finding (e.g. pregnancy, other exclusion criteria) considered to present a safety concern to continued treatment with the medical device, and warrants treatment withdrawal.
- Lost to follow-up.

The principal investigator and/or sponsor reserves the right to terminate the study for any reason.

4.3 Replacement Policy

Patients who are withdrawn from the study will not be replaced.

4.4 Lifestyle Guidelines

There are no special requirements as this is a non-interventional study.

4.5 Contraception

There are no special requirements as this is a non-interventional study.

4.6 Pregnancy Testing

Pregnancy testing will be at the discretion of the investigator and as per site's routine practice.

5 STUDY TREATMENT

5.1 Investigational Medical Device

This NIS refers only to the regular prescription of commercially available Cystistat according to the instructions for use (13).

Cystistat is a clear colourless solution presented in a 50 mL glass vial containing 40 mg sodium hyaluronate. It is manufactured by Mylan [REDACTED] and distributed by third companies in some countries.

5.2 Administration of Investigational Medical Device

Cystistat will be instilled into the bladder according to the instructions for use (13). Instillation is intended to be performed by a qualified healthcare professional with the use of a sterile catheter and sterile syringe using appropriate hygienic technique, to minimize risk of infection.

At instillation, the clinician will check that the content of the instructions for use (13), warnings and precautions especially, are followed before and during each treatment.

If in accordance with routine clinical practice at the site, a single-shot oral antibiotic will be given on instillation day.

In the event of any incident, the CRA, or sponsor study contact should be contacted immediately, and the event must be reported as described in Section 10.4.1.

5.3 Supply of Investigational Medical Device

Commercially available Cystistat will be prescribed as per routine clinical practice (i.e., the investigational medical device will not be supplied by the sponsor).

5.4 Storage, Disposition of Unused Investigational Medical Device and Accountability

Not required in this non-interventional study.

5.5 Randomization

Not applicable.

5.6 Breaking the Blind

Not applicable.

5.7 Rescue Medication

Not applicable.

5.8 Concomitant Medications

It is not required to collect all concomitant medication taken during this non-interventional study. The use of IC/BPS medication, pain medication, and other relevant concomitant medication (e.g. if in context with an adverse event or incident) will be captured by the patient in the diary card and the investigator will provide documentation in the eCRF, including at least indication, daily dose, and start and stop dates of administration.

5.9 Treatment Compliance

Not applicable.

5.10 Therapy at End of Study for Compassionate Use

Not applicable.

6 STUDY CONDUCT

When the clinical decision has been made to prescribe Cystistat for the first time to a patient according to the instructions for use (13), the investigator will consider enrolling the patient into this NIS. The decision to prescribe Cystistat must be previous and independent from the decision to include the patient in the NIS.

Patients eligible for study recruitment will have the nature, purpose, and risks of the study explained to them by the investigator. They will be provided with a written copy of the informed consent form (ICF) for the study and given sufficient time to consider the study's implications before deciding to participate. Patients agreeing to participate in the study will sign the ICF and be given a duplicate copy before recording any personal data.

In cases where the patient does not return to the next routine treatment, the site should make every effort to contact the patient so that they can appropriately be withdrawn from the study. All contact attempts should be documented in the patient's medical record. Should the patient continue to be unreachable, then she will be considered to have withdrawn from the study as "Lost to Follow-up." For all other patients withdrawing from the study, an alternative reason for discontinuation should be recorded in the eCRF. Patients may voluntarily withdraw from the trial for any reason and at any time.

In this NIS, the intended duration of observation per patient is approximately 6 months after start of treatment (irrespective of the duration of treatment). For details and timings of assessments, refer to [Section 7.0](#) and [Table 0-1](#).

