2 OBJECTIVES AND ENDPOINTS

2.1 Objectives

2.1.1 Primary Objective

To collect data on the performance of Cystistat on patients' overall IC/BPS condition at end of treatment or latest at week 12 in routine clinical practice.

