6.1 Baseline (before first treatment)

Patients for whom Cystistat is prescribed by the treating investigator will be enrolled in the study after signing a written informed consent form. No personal data will be recorded for the study before the consent procedure. Once eligible patients provide written informed consent, baseline assessments will be completed (this may be performed on the first treatment visit prior to instillation of Cystistat according to routine clinical practice):

- The investigator will review and document the patient's demography and medical history. This includes patients' demographic and anamnestic background data, diagnostic criteria of IC/BPS diagnosis, and previous and current treatments.
- Patients will be asked to complete the Bladder Pain/ Interstitial Cystitis Symptom Score (BPIC-SS). If the score is ≤ 18 , the patient will not be suitable for entering this NIS.
- The investigator will evaluate if the patient meets the inclusion/exclusion criteria.
- Patients will be asked to complete the Visual Analogue Scale (VAS) for bladder pain, urinary urgency, and quality of life (QoL).
- The investigator will assess and record any adverse events that occurred during this visit after signing the informed consent form.
- The investigator will provide the patient with the diary card and instruct her on how to record study related data at home. The following assessments are to be filled out by the patient:
 1. Morning voiding volume (once a week, preferably on the treatment day)
 2. Urinary voids and the respective volumes over a period of 24 hours (once a week, preferably starting the day before the treatment day)
 3. Use of concomitant IC/BPS medication, pain medication, and other relevant concomitant medication
 4. Adverse events
- A date for the next visit for the first treatment with Cystistat will be arranged and the investigator will remind the patient not to forget to take the diary card with her that day (not required if the first treatment with Cystistat is performed during the same visit according to routine clinical practice).
- The investigator will enter all required data from this visit in the eCRF within 5 business days.

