5.2 Analysis Population**5.2.1 Enrolled population**

The enrolled population includes all patients that have signed the ICF for this study.

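### No rule requires the study to be offered to every eligible newly prescribed patient, and those not approached or declining are not counted, so the responder rate cannot be shown to represent routine practice

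*Protocol*

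**What the plan says.** The primary objective (Protocol 2.1.1) is to collect performance data "at end of treatment or latest at week 12 in routine clinical practice". There is one treatment group (SAP 4.4), and the primary result is the number of responders divided by the number in the FAS, with a 90% confidence interval (SAP 7.1).

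On entry to the study, Protocol section 6 protects the prescribing decision: "The decision to prescribe Cystistat must be previous and independent from the decision to include the patient in the NIS". For the enrolment decision it says that "the investigator will consider enrolling the patient into this NIS". The next paragraph has the investigator explain the study to patients who are eligible for recruitment. Section 6.1 adds: "Patients for whom Cystistat is prescribed by the treating investigator will be enrolled in the study after signing a written informed consent form".

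One exclusion criterion (Protocol 4.2.2) is a matter of judgement: "Patients are not able to fulfil study requirements according to physician's opinion". Recruitment across sites is described in Protocol 3.1: "The recruitment will be competitive, with a maximum of approximately 15 patients per site".

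The widest population in the SAP begins at consent (5.2.1): "The enrolled population includes all patients that have signed the ICF for this study".

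**The concern.** The physician who prescribes also decides whether to raise the study with the patient. The first decision must be independent of the study. The second carries no matching requirement, and it leaves no record unless the patient signs consent.

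In a one-arm study there is no comparison group in which the same selection would largely cancel. If patients who are approached differ in expected outcome from those who are not, the difference goes straight into the responder rate, and the 90% interval does not reflect it. The study is meant to support the benefit/risk profile and conformity with the Medical Device Regulation (Protocol 3.2). A reader of the report will want to know what share of newly prescribed patients the rate describes, and the planned data cannot answer that.

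**Working it through.** **1. Does any text require an offer to all, or count those not enrolled?**

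- Protocol 6, first paragraph: enrolment is something the investigator considers. There is no consecutive or all-patient rule.
- Protocol 6, second paragraph: eligible patients have the study explained. This is the nearest text to an all-comers rule. It follows the discretionary step, and eligibility itself includes the physician's judgement under 4.2.2.
- Protocol 6.1: prescribed patients are enrolled, but conditional on signed consent. It does not say that each is asked.
- Protocol 6.1 also bars recording personal data before consent. An anonymous count would be compatible with this but is not requested.
- Protocol 9.5: the minimum content of central monitoring is enrolment, completion, safety and key data. No count of patients not enrolled is named.
- Protocol 9.6.2: the site archive list includes a patient identification list but no screening log.
- SAP 5.2.1: the widest population is patients with signed consent.

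Both gaps are therefore present in the two documents.

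**2. The plan's own figure.** The total of 74 includes 7 for dropout, so 74 − 7 = 67 evaluable. Then 67 × 1.10 = 73.7, which rounds up to 74; dividing instead, 67 / 0.90 = 74.4, gives 75. The derivation of 67 is redacted. The sample size is not in dispute here; 67 is used below only to scale the illustration.

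**3. Illustration of selection (all selection inputs are assumed).** Let p be the response rate in all eligible first-prescription patients, and k the chance that a future responder is offered the study relative to a future non-responder. With equal consent among those offered:

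enrolled rate = p·k / (p·k + 1 − p)

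- p = 0.60, k = 1.5: 0.90 / (0.90 + 0.40) = 0.69, up 9 points.
- p = 0.60, k = 1/1.5: 0.40 / (0.40 + 0.40) = 0.50, down 10 points.
- p = 0.60, k = 1: 0.60, no shift.

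**4. A second way to set it out.** Let f be the share of eligible patients passed over, and d the response rate in those enrolled minus that in those passed over. The shift is f·d.

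- f = 20%, d = 20 points: 4 points.
- f = 30%, d = 30 points: 9 points.
- f = 40%, d = 30 points: 12 points.

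**5. Scale against the planned precision.** At p = 0.60 and n = 67, the 90% half-width by normal approximation is 1.645 × √(0.60 × 0.40 / 67) = 0.098, or 9.8 points. The SAP's interval method is redacted, so an exact (Clopper-Pearson) 90% interval was used to check coverage of a true 60%:

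| Upward shift (points) | Coverage |
|---|---|
| 0 | 92% |
| 4 | 87% |
| 6 | 80% |
| 9 | 63% |
| 12 | 41% |

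A shift of the assumed size would be comparable with the whole sampling uncertainty. Nothing in the documents says whether such a shift occurs.

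**The case against.** The strongest reply is that the protocol, read as a whole, already intends an all-comers approach: eligible patients are to have the study explained, and prescribed patients are to be enrolled once they consent. That reading is reasonable, and the wording is at worst ambiguous. It does not settle the matter, because the first step is still discretionary and, with no denominator, adherence to the generous reading could not be checked.

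Four stronger readings are tempting, and the documents do not support them.

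- *The result cannot be called routine practice.* Prescription comes first and is independent of inclusion, the product is commercial, and treatment follows usual care. What is missing is evidence that enrolled patients represent all who are newly prescribed.
- *The protocol lets sites choose likely responders.* The physician's-opinion exclusion concerns ability to meet study requirements, not prognosis. Only first prescriptions qualify, and known GAG substitution therapy within the last 2 years is excluded, so there should be no recent response to this class to select on. Competitive recruitment does not itself favour good-prognosis patients; where recruitment is difficult it may push sites to take everyone. The site cap would let five sites supply all 74 patients (5 × 15 = 75), but that is concentration across sites, not selection within them.
- *The rate is inflated by a known amount.* Both the size and the upward direction are assumed.
- *Selection could move the result into the 60–85% range.* That range is background on remission rates, not a stated comparator, and the sample-size basis is redacted.

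It is also fair to say that all analyses are declared exploratory, and that the monitoring plan and eCRF were not available and could contain a log. Neither the protocol nor the SAP refers to one.

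**Conclusion.** The concern holds in limited form. The documents neither require that every eligible first-prescription patient be approached nor count those not approached or declining. The uncontrolled responder rate therefore cannot be shown to represent all newly prescribed patients, and selection cannot be assessed in either direction.

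Its size is unknown. The figures of 69% and 50% at an assumed true 60% rest wholly on the assumed k and on equal consent among those offered. They show only that modest selection could matter on the scale of the 9.8-point half-width. The gap does not invalidate the study. It limits how far the primary result can be generalised and is cheap to address, so the change should be made.

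**What to change.** In Protocol section 6, replace the discretionary wording with a duty to offer participation to every consecutive patient with a first Cystistat prescription who appears eligible, until the site limit is reached.

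Have each site keep an anonymous tally, with no personal data, of:

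- first prescriptions in the recruitment period;
- not eligible before consent, by criterion, with physician's opinion shown separately;
- eligible but not offered, with reason;
- offered and declined;
- signed consent;
- failed eligibility after consent, for example a BPIC-SS of 18 or less.

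The last two are kept apart because the BPIC-SS is completed after consent, so patients who fail on it already belong to the SAP's enrolled population.

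In the SAP, report these counts by site in the disposition table, beside the responder rate.

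The planned study period ended in Q3 2023, and the SAP is dated 30 November 2023 and lists no protocol amendment. If enrolment has closed, the offer rule can no longer be applied. In that case obtain retrospective site counts of first prescriptions where feasible and state the limitation next to the primary result.

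The cost is one sentence in the protocol (by amendment), one tally sheet per site and one table. The sample size is unchanged. The downside is minor site effort and possibly a less favourable responder rate.
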